# Table of Contents

i. Updates from previous version (v1)	3
i.i. Medication persistence cut-off value	3
i.ii. Analyses of secondary outcomes related to the linked hospital care data	3
i.iii. Data imputations for key outcomes as sensitivity analyses	4
i.iv. Stratification of Kessler 6-item (K6) scale scores	4
i.v. CONSORT flow diagram	5
1. Study design	5
1.1 Purpose and scope	5
2. Analysis principles	6
3. Trial profile	7
3.1 Data sources and analysis samples	7
3.2 Cluster characteristics and baseline comparisons	8
3.3 Consumer participants' characteristics and baseline comparisons	8
4. Proposed outcome analysis	.10
4.1 Primary outcome	.10
4.2 Secondary outcomes	.11
4.3 Other outcomes	.15
5. Appendix: Proposed figures and results tables	.16
References	.24

- i. Updates from previous version (v1)
- i.i. Medication persistence cut-off value

The cut-off value for defining non-persistence was changed to 30 days delay in medication refills. Other processes involved in the primary outcome calculations illustrated in the SAP (section **4.1.1**) remained unchanged. The original cut-off value was adapted from a systematic review in which authors found studies had adopted various values for defining the medication non-persistence ranging from 14 – 120 days (Sattler, Lee, & Perri, 2013). Psychotropic medications such as antipsychotics, antidepressants, and mood stabilisers as well as medications for other long-term health conditions such as antithrombotic agents, and medications for diabetes, cardiovascular disease, and obstructive airway diseases, were included in this analysis. After comprehensive data preparation and curation, the preliminary descriptive analysis found the average days of supply of these prescriptions were around 34 days (**Table i**). Therefore, a 30-day refill gap was applied in defining medication persistence, which meant participants were approximately skipping a repeat prescription (refill), and would likely be classified as non-persistent with their medications.

Table I Average days of supply per medication group

Medication Group	Number of	Days of Supply,
	Prescriptions	Mean (SD)
Antidepressants	4143	29 (8.4)
Antipsychotics	3930	34 (17.0)
Mood stabilisers	1541	53 (33.6) *
Antithrombotic agents	169	29 (1.0)
Medications used for diabetes	893	36 (17.5)
Medications used for cardiovascular diseases	3248	33 (12.3)
Medications used for obstructive airway diseases	307	31 (11.6)
All groups	14231	34 (18.1)

\* standard pack sizes and Pharmaceutical Benefits Scheme quantities are larger for mood stabilisers than other medications of interest

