### i.ii. Analyses of secondary outcomes related to the linked hospital care data

A secondary outcome of the RCT is to examine differences in hospital admissions or emergency department visits between the intervention group and the comparator group. However, almost three quarters of participants had no record of hospital admissions and/or emergency department visits. The mixed-effects negative binomial models were not appropriate due to a lack of convergence and effective sample size. Mixed-effects logistic regression model was used to compare the difference in hospital admission between RCT groups. A mixed-effects negative binomial regression model was

further applied to explore the difference in the number of hospital admissions between RCT groups among those who had at least one hospital admission. The same analytic approach was applied to analyse the emergency department visit outcome and mental health-related hospital admission and emergency department visit outcomes. This approach was listed as potential analytical methods based on data suitability and assumptions in the original SAP.

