#### 1.1 Purpose and scope

The purpose of this document is to minimise bias by defining and making publicly available our analysis approach prior to reviewing or analysing any trial data. The following statistical analysis plan (SAP) has been developed to inform the analysing and reporting of the main outcomes from the *PharMIbridge* RCT including our approach to expected protocol deviations, withdrawals, missing data, and loss to follow up. Outcomes considered in this SAP are the primary and key secondary outcomes that will inform both the main effectiveness findings of the trial and future Medical Services Advisory Committee (MSAC) applications. In this SAP, broad statistical analysis principles are outlined, primary and secondary trial outcomes are described, along with appropriate methods for statistical comparison. Other outcomes, such as those related to the *PharMIbridge* training program outcome and qualitative data analysis will be reported elsewhere. This SAP should not be taken as a comprehensive plan for all future analyses using RCT data.

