**Primary analysis:** A mixed-effects logistic regression model will be applied to compare the medication's adherence rate over the 6 months after initial intervention/comparator service between IG and CG. RCT group will be entered as fixed effect and pharmacy entered as a random intercept to account for possible non-independence of observations from participants who attend the same pharmacy. The baseline value of the outcome variable will be included as a covariable in the model. The effect estimate will be reported as an odds ratio with 95% confidence interval.

**Sensitivity analysis:** To assess the robustness of the results, sensitivity analysis will be performed for this primary outcome, using the linked PBS data sample.

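### The 30-day refill-gap rule in the objective co-primary outcome was set after trial data had been described, yet section 1.1 claims otherwise and no planned analysis uses the v1 cut-off

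*SAP*

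**What the plan says.** Section 4.1.1 makes the objective co-primary outcome binary. A participant is non-adherent if the average medication possession ratio (MPR) is below 80%, or if any refill is more than 30 days late.

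Section i.i records that this rule is new in version 2: "The cut-off value for defining non-persistence was changed to 30 days delay in medication refills". It also explains where the 30 days comes from. On the v1 value it says only this: "The original cut-off value was adapted from a systematic review in which authors found studies had adopted various values", with a range of 14 to 120 days. It then turns to the trial's data: "After comprehensive data preparation and curation, the preliminary descriptive analysis found the average days of supply of these prescriptions were around 34 days". The conclusion follows directly: "Therefore, a 30-day refill gap was applied in defining medication persistence".

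Section 1.1, on the purpose of the document, says that the approach is defined and made public "prior to reviewing or analysing any trial data". That sentence carries no qualification for version 2.

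Two other update sections show what had been done by the time version 2 was written. Section i.ii reports on the hospital outcomes: "The mixed-effects negative binomial models were not appropriate due to a lack of convergence and effective sample size". Section i.iii describes, in the past tense, multiple imputation of several outcomes, psychotropic adherence among them.

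For robustness of this outcome, section 4.1.1 says that "sensitivity analysis will be performed for this primary outcome, using the linked PBS data sample". Section i.iii adds the imputation analysis. Section 2 adds per-protocol and metropolitan/non-metropolitan analyses.

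**The concern.** A cut-off that decides who counts as adherent is part of the definition of a co-primary outcome. If it is altered after trial data have been examined, it cannot be presented as fixed in advance, however sensible the new value is. A reader who relies on section 1.1 would take the 30-day rule as pre-specified. Section 4.1.1 reinforces this, because it supports the rule only by citing the literature review, whereas section i.i says that the review supplied the v1 value and the trial's prescriptions supplied the new one.

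The usual protection is to show the result under both definitions. Here that protection is missing, and the v1 value is not given, so a reader could not even specify the comparison. Section 1.1 says that these results are to inform applications to the Medical Services Advisory Committee, so the status of the definition matters beyond the trial report.

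**Working it through.** **1. The plan's own figure.** Table i in section i.i gives prescriptions and mean (SD) days of supply for seven groups: antidepressants 4,143, 29 (8.4); antipsychotics 3,930, 34 (17.0); mood stabilisers 1,541, 53 (33.6); antithrombotics 169, 29 (1.0); diabetes 893, 36 (17.5); cardiovascular 3,248, 33 (12.3); obstructive airway 307, 31 (11.6).

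- Total N = sum of n = 14,231.
- Weighted mean = sum(n × mean) / N = 489,190 / 14,231 = 34.4 days.
- Combined SD = sqrt{[sum (n − 1)SD² + sum n(mean − 34.4)²] / (N − 1)} = 18.06.

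The table states 14,231 and 34 (18.1), so its summary row reproduces. The arithmetic behind the 30-day rule is sound; the issue is its timing and how it is described.

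**2. Timing.**

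| Place | What it shows |
|---|---|
| i.i | 30 days was adopted because of a description of curated trial prescriptions |
| i.ii | Negative binomial models for hospital outcomes had been tried and set aside |
| i.iii | Imputation of adherence is reported as done |
| 1.1 | Approach defined before any trial data were reviewed or analysed |

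The first three rows cannot be reconciled with the fourth as a statement about version 2.

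**3. Does any planned analysis vary the cut-off?**

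| Analysis | What it varies | Cut-off |
|---|---|---|
| Linked-PBS sample (4.1.1) | Data source | 30 days |
| Multiple imputation (i.iii) | Handling of missing data | 30 days |
| Per-protocol (section 2) | Participants included | 30 days |
| Metropolitan or not (section 2) | Subgroup | 30 days |

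The SAP names no other cut-off for any of these, so none shows the result at the v1 value.

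**4. Can the effect of the change be computed?** No. The v1 value and the adherence rates are both absent. A v1 value below 30 days would mean that the rule was loosened, and one above 30 that it was tightened; the cited range of 14 to 120 days allows either.

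**5. What the gap rule can add to the MPR rule (illustration only).** Assume a 182-day window, one gap in one class, full supply otherwise, and MPR averaged over k classes. Average MPR reaches 80% at a gap of 0.2 × k × 182 days:

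- k = 1: 36.4 days
- k = 2: 72.8 days
- k = 3: 109.2 days

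Under these assumptions, gaps of 31–36, 31–72 and 31–109 whole days respectively are non-adherent through the refill rule alone. The cut-off can therefore decide a participant's classification. These bands do not measure the effect of moving from the v1 value to 30 days.

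**6. Fit of the rationale by class.** The stated idea is that a 30-day gap is roughly one missed repeat. Dividing 30 by mean supply gives 30/29 = 1.03 for antidepressants, 30/34 = 0.88 for antipsychotics and 30/53 = 0.57 for mood stabilisers. Over the three psychotropic groups the mean is 335,440 / 9,614 = 34.9 days. Mood stabilisers are 1,541 / 9,614 = 16% of those prescriptions.

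**The case against.** The change is disclosed at the front of the document, with its reason and data, and section 4.1.1 is consistent with it. Table i describes days of supply per prescription, pooled over arms and over seven drug groups, four of them not psychotropic. It contains no refill gaps, no adherence rates and no comparison of arms. The models in section i.ii concern hospital outcomes, and section i.iii concerns missing data. All of this stands.

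A reader might infer that the cut-off was picked with adherence by arm in view. The SAP does not show that. Section i.iii says imputation was run separately by randomised group, so arm-labelled adherence data were in use by the time version 2 was written, but the order of the version 2 changes is not stated. Nor does the SAP say that those who chose 30 days were blind to allocation. The question is open, not answered against the sponsor.

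A reader might also take section 1.1 as claiming that the 30-day value itself was fixed in advance. It does not name the cut-off; it is a general statement carried over without qualification, and one added sentence would cure it. Until then, it misdescribes this version.

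Nor can the refill rule be called the dominant part of the composite. The SAP gives no distribution of gaps or of classes per participant, and for a one-class user the illustrative band is only 31–36 days.

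On mood stabilisers, the footnote to Table i already concedes that "standard pack sizes and Pharmaceutical Benefits Scheme quantities are larger for mood stabilisers than other medications of interest", the text claims only approximate correspondence, and the psychotropic-only mean of 34.9 days is close to the pooled 34. A uniform gap is a legitimate choice, so the uneven fit is grounds for an optional analysis and is not an error.

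Disclosure in section i does not, however, correct section 1.1 or supply the missing comparison.

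**Conclusion.** The point holds. The refill-gap component of the objective co-primary outcome was set in version 2 after the trial's own prescriptions had been described. Section 1.1 is untrue of that version, and none of the four other analyses of the outcome tests dependence on the cut-off. Because the v1 value is missing, the effect of the change on the result is unknown in both size and direction. The bands in the working show only that a refill rule can settle classification by itself, under stated and simplified assumptions.

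The conclusion does not rest on any suggestion of a choice informed by arm, and it does not imply that 30 days is a poor value. The descriptive basis may well justify keeping it. What needs correcting is how the rule is labelled and the absence of a result at the v1 cut-off. Since a co-primary outcome is affected, this should be settled before the result is presented as pre-specified.

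**What to change.** 1. In section 1.1, state that the non-persistence cut-off was modified after trial data had been reviewed. Give the date of the change, and say whether those who chose the value had seen any results by arm.
2. In section 4.1.1, state the v1 cut-off. Report the same mixed-effects logistic model at that value beside the 30-day result, and label the 30-day definition as modified after data review. Point the justification to section i.i as well as to the literature review.
3. Optional: add a sensitivity analysis in which the permitted delay scales with the days of supply of the preceding fill, so that a missed repeat means the same in each class.

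Items 1 and 2 cost a few sentences and one further run of an existing model, plus a less favourable pre-specification statement. Item 3 needs a second run, with gaps recoded.

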### i.ii. Analyses of secondary outcomes related to the linked hospital care data

A secondary outcome of the RCT is to examine differences in hospital admissions or emergency department visits between the intervention group and the comparator group. However, almost three quarters of participants had no record of hospital admissions and/or emergency department visits. The mixed-effects negative binomial models were not appropriate due to a lack of convergence and effective sample size. Mixed-effects logistic regression model was used to compare the difference in hospital admission between RCT groups. A mixed-effects negative binomial regression model was

further applied to explore the difference in the number of hospital admissions between RCT groups among those who had at least one hospital admission. The same analytic approach was applied to analyse the emergency department visit outcome and mental health-related hospital admission and emergency department visit outcomes. This approach was listed as potential analytical methods based on data suitability and assumptions in the original SAP.

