#### 4.2 Secondary outcomes

Secondary outcomes will be the differences in the following variables between IG and CG at the 6-month follow-up point or during the six months after the initial intervention/comparator service. Different samples will be used to analyse the secondary outcomes based on the data required for each specific analysis.

Overall, for binary and ordinal outcomes, mixed-effects logistic/ordered logistic regression models will be applied to compare these outcomes between the intervention and comparator groups. For continuous outcomes, mixed-effects linear regression models will be applied; and for count data, mixed-effects Poisson regression models will be used. In all mixed-effects models, the treatment arm will be entered as a fixed effect and the pharmacy will be entered as a random intercept to account for possible non-independence of observations from participants who attend the same pharmacy. Baseline values of the outcome variable will be included as a covariate in these models when possible. Between-group comparisons will be reported as mean difference, odds ratio or incidence rate ratio with 95% confidence intervals.

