#### 4.2.1 Secondary outcomes using the linked MBS/PBS data and pharmacy dispensing history data

**Data and participants:** The full analysis sample for secondary outcomes regarding medication adherence for other chronic diseases and healthcare utilisations will be the combination of linked MBS/PBS data and pharmacy dispensing history data.

Table 4.1 Variables and proposed analyses using linked MBS/PBS data and pharmacy dispensing history data

Variables	Coding	Statistical analysis	Effect estimate
Medication adherence for medications for other chronic	1=Adherent, 0=Non-	Mixed-effects logistic regression	Odds ratio and 95% CI
conditions	adherent	-	
General practitioner visits during the six months after the initial intervention/comparator service interview	-	Mixed-effects linear regression (consider other models, such as negative binomial model if model	Mean difference and 95% CI
		assumption is not met)	

4.2.2 Secondary outcomes using the linked hospital data

**Data and participants:** The full analysis sample for secondary outcomes relating to healthcare service utilisation will be the linked hospital data sample.

Table 4.2 Variables and proposed analyses using linked hospital data

Variables	Coding	Statistical analysis	Effect estimate
All-cause hospital admissions	-	Mixed-effects logistic	Mean difference
during the six months after the		regression and mixed-	and 95% CI
initial intervention/comparator		effects negative	
service		binomial models	
Mental health-related hospital	-	Mixed-effects linear	Mean difference
admissions during the six months		logistic regression and	and 95% CI
after the initial		mixed-effects negative	
intervention/comparator service		binomial models	
All-cause emergency department	-	Mixed-effects linear	Mean difference
admissions during the six months		logistic regression and	and 95% CI
after the initial		mixed-effects negative	
intervention/comparator service		binomial models	
Mental health-related emergency	-	Mixed-effects linear	Mean difference
department admissions during the		logistic regression and	and 95% CI
six months after the initial		mixed-effects negative	
intervention/comparator service		binomial models	

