# **Table 5.3 Primary outcomes**

	N	Intervention ( PharMlbridge )		N	Comparat (MedsChe		Between group difference at follow-up	P-value
		Baseline	Follow-up		Baseline	Follow-up	Mean difference/Odds ratio (95% CI)	
Subjective adh Adherence to psychotropic medications, n (%)	nerence	e measure us	sing linked PB	S data	and pharm	acy dispensi	ng history data	
Objective adherence to medications (RAM), mean (SD)	erence	measure usi	ing survey cor	mpleti	on data			

Table 5.4 Secondary outcomes using survey data

Variables	N	Intervention (PharMIbridge)		N	Comparato	r (MedsCheck)	Between group difference at follow-up	P-value
		Baseline	Follow-up		Baseline	Follow-up	Mean difference/Odds ratio (95% CI)	
Quality of life, mean (SD)								
Independent living								
Relationship								
Mental health								
Coping								
Pain								
Senses								
Illness beliefs, mean (SD)								
Risk of non-specific								
psychological distress, mean								
(SD)								
High risk of non-specific								
psychological distress, n (%)								
Treatment burden, n (%)								
No burden								
Low burden								
Medium burden								
High burden								
Attitudes to therapy, n (%)								
Sleep issue, n (%)								
Non-clinical insomnia								
Sub-threshold								
Moderate clinical								
insomnia								
Severe clinical insomnia								
Physical activity								
recommendations met, n (%)								

Variables	N	Intervention ( PharMIbridge )		N	Comparato	r (MedsCheck)	Between group difference at follow-up	P-value
		Baseline	Follow-up		Baseline	Follow-up	Mean difference/Odds ratio (95% CI)	
Alcohol use, n(%)								
Tabacco use, n(%)								
Risk assessment for								
Cardiovascular disease in								
previous 6 months								
Glycated hamoglobin (HbA1c)								
measured in previous 6								
months								

Table 5.5 Secondary outcomes using linked MBS/PBS data and pharmacy dispensing history data

	N	Intervention ( PharMIbr		N	Compara (MedsCh		Between group difference at follow-up	P- value
		Baseline	Follow-up		Baseline	Follow-up	Mean difference/Odds ratio (95% CI)	
GP visits, mean (SD) Adherence to medications for other chronic conditions, n (%)								

\*GP, general practitioner

Table 5.6 Secondary outcomes using linked hospital data, mean (SD)

	N	Intervention ( PharMIbridge )		N	Comparator (MedsCheck)		Between group difference at follow-up	P- value
		Baseline	Follow-up		Baseline	Follow-up	Mean difference (95% CI)	

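### The exploratory hospital and ED count comparison is confined to participants who had an event, and Tables 4.2 and 5.6 list only a mean difference for models that give odds and rate ratios

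*SAP*

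**What the plan says.** Section i.ii describes the current analysis of the linked hospital data. It reports that "almost three quarters of participants had no record of hospital admissions and/or emergency department visits" and gives this as background to abandoning the full-sample count model: "The mixed-effects negative binomial models were not appropriate due to a lack of convergence and effective sample size". Two steps replace it.

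- Any event or none: "Mixed-effects logistic regression model was used to compare the difference in hospital admission between RCT groups". No restriction to event-havers is stated.
- Number of events: a mixed-effects negative binomial model "further applied to explore the difference in the number of hospital admissions between RCT groups among those who had at least one hospital admission".

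The scope is wide: "The same analytic approach was applied to analyse the emergency department visit outcome and mental health-related hospital admission and emergency department visit outcomes".

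Section 4.2.2 names the linked hospital data sample as the full analysis sample. Table 4.2 lists logistic and negative binomial models for all four outcomes without the event restriction, and its effect-estimate column reads mean difference with 95% CI in every row. Table 5.6 provides mean (SD) per arm and a mean difference column. Tables 5.3 to 5.5 each head that column mean difference/odds ratio. The general text of section 4.2 allows a mean difference, an odds ratio or an incidence rate ratio. Section 2 places all analyses under intention to treat.

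**The concern.** There are three linked problems.

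1. **The subset.** Whether a participant has an admission or ED visit in the six months after the first service is something the service may change. If it prevents some people from having any event, those left with events in the intervention arm differ in kind from those in the comparator arm. The allocated labels are kept, but participants are dropped because of an outcome, which is what intention to treat is meant to avoid.
2. **The distribution.** Counts among event-havers start at one. A standard negative binomial gives positive probability to zero. The SAP does not say whether a truncated form is used.
3. **The effect measure.** A logistic model yields an odds ratio and a negative binomial model a rate ratio. No step is described that would turn either into a mean difference, and Table 5.6 has no column for the odds ratio, which is the randomised result.

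Section 1.1 says the outcomes in this SAP inform the main effectiveness findings and future Medical Services Advisory Committee (MSAC) applications, so a diluted count ratio or a mislabelled effect could be carried into that use.

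**Working it through.** The SAP gives no event counts, sample size or power for these outcomes, so there is no figure of its own to reproduce. What follows is an illustration.

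**Inputs.** Comparator share with zero events: 75%, assumed, prompted by the almost three quarters in section i.ii. True rate ratio: 0.70, assumed. Counts: Poisson, or negative binomial with size k = 1.0, 0.5 or 0.3, assumed.

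**Formulas.** With mean m:
- Poisson: P(0) = exp(−m), so m = −ln 0.75 = 0.288.
- Negative binomial: P(0) = (1 + m/k)^(−k), so m = k(0.75^(−1/k) − 1).
- Mean among event-havers = m / (1 − P(0)).
- Variance among event-havers = (Var + m²)/(1 − P(0)) − (mean among event-havers)².
- Standard-error factor if a Poisson-type variance is assumed = √(mean/variance) among event-havers.

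**Poisson case in full.** Intervention mean = 0.7 × 0.288 = 0.201, and P(any) = 1 − exp(−0.201) = 0.182. Means among event-havers are 0.288/0.25 = 1.151 and 0.201/0.182 = 1.104, ratio 0.96. The comparator variance/mean among event-havers is 0.137, and √(1/0.137) = 2.70.

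| Counts | Overall mean, comparator / intervention | Any event | Odds ratio, any event | Mean among event-havers | Ratio among event-havers | Variance/mean | SE factor |
|---|---|---|---|---|---|---|---|
| Poisson | 0.288 / 0.201 | 25.0% / 18.2% | 0.67 | 1.151 / 1.104 | 0.96 | 0.14 | 2.70 |
| k = 1.0 | 0.333 / 0.233 | 25.0% / 18.9% | 0.70 | 1.333 / 1.233 | 0.93 | 0.33 | 1.73 |
| k = 0.5 | 0.389 / 0.272 | 25.0% / 19.5% | 0.73 | 1.556 / 1.394 | 0.90 | 0.61 | 1.28 |
| k = 0.3 | 0.483 / 0.338 | 25.0% / 20.3% | 0.76 | 1.931 / 1.668 | 0.86 | 1.16 | 0.93 |

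A true 30% reduction therefore shows as 4% to 14% among event-havers, while the any-event odds ratio of 0.67 to 0.76 still shows the benefit.

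**The direction can also reverse.** Assume 74% zeros in the comparator arm, 10% frequent users averaging 2.5 events, and a service that halves the rate only in the other 90% (0.207 to 0.103). Overall means are 0.25 + 0.9 × 0.207 = 0.436 and 0.25 + 0.9 × 0.103 = 0.343, ratio 0.79. Event-havers are 26.0% and 18.0%. Their mean counts are 1.68 and 1.90, ratio 1.13, because frequent users rise from 35% to 51% of intervention event-havers.

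**Truncation.** One large simulation without clustering (40,000 per arm, 74% zeros in the comparator arm, k = 0.5, true ratio 0.50) compared three fits. An ordinary negative binomial on event-havers gave 0.82 and put 23% fitted probability on impossible zeros. A zero-truncated one gave 0.51. A negative binomial on everyone gave 0.49.

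**The case against.** The strongest reply is that the SAP's first comparison is sound. The any-versus-none logistic model carries no event restriction, and the count step is only said to explore. That stands. A reader might infer that none of the hospital and ED effects is a randomised comparison, or that a real benefit would go unseen. The SAP does not support either: the logistic analysis keeps everyone and, in the table above, shows the benefit.

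Other tempting readings also go too far.

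- **That the model is untruncated.** The SAP is silent, so the fair statement is that truncation is not specified. Even an ordinary negative binomial estimates the ratio of means among event-havers, though not the underlying rate ratio.
- **That standard errors are 2.7 times too large.** That is the pure Poisson extreme. The factor falls to about 0.9 with strong overdispersion.
- **That each count model uses a quarter of participants.** The almost three quarters refers to admissions and/or ED visits together. No share is given by outcome or by arm.
- **That refitting the rejected model in a subset is a contradiction.** The subset removes the zeros that section i.ii describes just before reporting the failure. The smaller sample is a cost in precision, not an inconsistency.
- **That the Poisson default in section 4.2 creates a conflict.** It is a general rule that the outcome-specific tables override.

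On the effect measure, section 4.2 does foresee odds and rate ratios, and three rows of Table 4.2 carry the hybrid term linear logistic, which suggests wording left unrevised. This makes the point a contradiction within the SAP, not a settled decision to print only mean differences. It still needs correcting.

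**Conclusion.** The point holds for the exploratory count comparison and for the effect-measure entries in Tables 4.2 and 5.6, across all four hospital and ED outcomes. The count comparison conditions on a post-randomisation outcome and departs from the SAP's own intention-to-treat principle and stated analysis sample. At an assumed 75% zeros and true rate ratio of 0.70 it would show about 0.86 to 0.96. The misfit of a Poisson-type standard error would be about 0.9 to 2.7 times, depending on overdispersion. These sizes rest on assumed distributions that ignore clustering, not on trial data. The any-event logistic comparison and the co-primary adherence outcomes are not affected. This should be fixed, but it does not threaten the trial's main conclusion.

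**What to change.** 1. In section i.ii and Table 4.2, name the logistic odds ratio in the full linked hospital sample as the randomised result, with n (%) having any event in each arm.
2. Estimate the count effect in the same full sample with a log-link negative binomial or Poisson model and standard errors clustered on pharmacy, reported as an incidence rate ratio. This removes the pharmacy random intercept from the count model.
3. If an event-only count model is kept, make it zero-truncated and label it descriptive and non-randomised.
4. In Tables 4.2 and 5.6, replace mean difference with odds ratio and incidence rate ratio, each with its 95% CI.
5. Because section i.ii is written after the data were inspected, date the added rate model and mark it as such.

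The cost is SAP wording and a few lines of code, with no new data. The rate ratio becomes population-average instead of pharmacy-specific. Cluster-robust errors need enough pharmacies or a small-sample correction, and the SAP does not give the number of pharmacies. With few events the interval may be wide, which should be reported as it is.
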